## PROTOCOL SYNOPSIS

Investigation: Tailored information about the coronavirus SARS CoV2, Covid-19, the coronavirus pandemic, the coronavirus infodemic and digital sources of reliable health information for patients with chronic kidney disease stage 4-5, using information videos followed by a teach-back method. The research questions is whether tailored information followed by the teach-back procedure improves health literacy and digital health literacy, reduce anxiety, maintain self-perceived health and lower the risk of Covid-19. We will utilize updated reliable health information at the LNT website lnt.no and the Norwegian Health Authority websites helsenorge.no, fhi.no and imdi.no. The teach-back method will be used in the intervention group only, which aims to ensure that key messages in information videos are presented in a way that the patient can understand, correct any misconceptions and show strategies to critically assess digital health information.

Target population: Patients with advanced kidney disease (CKD stage 4 or 5).

Centre(s): Akershus University Hospital, Lørenskog, Norway.

Study Period: Estimated date of first patient enrolled: 07.12.20, and date of last patient completed: 31.12.23.

Main Endpoints: 

- Digital literacy, measured by eHEALS.
- Health literacy, measured by HLQ.
- Degree of concern for Covid-19, measured by Fear of corona scale.
- Self-perceived health, measured by EQ-5D-5L.

Design: Randomized prospective open clinical trial.

Inclusion Criteria: Age  $\geq$  18 years.  
CKD stage 4 or 5, including renal transplant recipients (defined as CKD5T).  
Written informed consent.

Exclusion Criteria: Positive SARS CoV2 test prior to the baseline visit or at the baseline time-point.  
Cognitive impairment.  
Any reason why, in the opinion of the Investigator, the patient should not participate.

Sample Size: n = 192, where we aim for inclusion of  $\geq$  50 patients with other native tongue than English or a Scandinavian language (Norwegian, Swedish or Danish).

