#### 4.1.1 Flowchart

	Screening and Baseline visit	Within next 7 days	3 (-4) month Final visit	24 month follow-up
Screening for inclusion in trial	•			
Eligibility assessment and study enrollment	•			
Obtaining written informed consent	•			
Semi-structured interview	•		•	
eHEALS, a measure of digital health literacy	•		•	
HLQ, a measure of functional, interactive and critical literacy	•		•	
Fear of corona scale, anxiety / concern for Covid-19	•		•	
EQ-5D-5L, self-perceived health	•		•	
Question: Difficulty finding information in native tongue	•		•	
Question: Feeling overwhelmed by Covid-19 information	•		•	
Interviewer's assessment of Clinical Frailty Score	•		•	
Randomization	•			
Presentation of websites, including LNT information videos	•			
Study intervention (teach-back method)		•		
Medical record assessment	•			•
Charlson comorbidity index	•			

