#### 4.1.2 Study Visits, Assessments, Data Recording and Investigator Delegation Procedure

Three study visits will be performed as presented in the flowchart. The Investigators will conduct a semi-structured interview and fill in an electronic CRF, which will be dated to ensure correct follow-up time, and to correct for events occurring during the study period that might influence participant responses. Data will be recorded directly into the electronic CRF at the baseline and final visits.

At the baseline visit a semi-structured interview will be performed, followed by a presentation of the LNT website (21). By early December 2020 this website will contain 20 short videos with information tailored for patients with CKD and organ transplant recipients on the topics SARS CoV2, Covid-19, the coronavirus pandemic, the coronavirus infodemic and strategies to critical assess of available digital sources of health information. These videos also contain a short presentation of updates reliable health information sources at the Norwegian Health Authority websites fhi.no, helsenorge.no and imdi.no (1, 6, 7), included where they can find information translated to various languages and where they can find links to other reliable digital health information sources at these websites. The videos are created by the study group and will be filmed and edited at Akershus University Hospital. They will be made originally in Norwegian and English, followed by translation and dubbing to several other languages, similar to previous patient information projects at Akershus University Hospital (22). All study participants will be presented to this source of health information at baseline and asked to study it closely.

For patients randomized to the *control group*, the Investigator will present them with the information videos available at the LNT website (21) and the Norwegian Health Authority websites (1, 6, 7), which would be regarded as within the frame of standard care, although this service is seldom provided at present.

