For patients randomized to the *intervention group*, the Investigator will take on a more active part and make a new appointment with the patient (a new study visit) within 7 days following the baseline visit, either as a regular meeting, a digital meeting (e.g. zoom) or a telephone meeting. The patient will be asked to seek information available at the LNT website and watch the information videos found at this website, plus seek information available at the Norwegian Health Authority websites, before the new study visit. At the study visit the patient will be asked to give a short resume of take home messages from these websites that he/she find useful in everyday life. They will be asked if they have any questions regarding the information presented at these websites, followed by a teach-back procedure, which aims to ensure that key messages are presented in a way that the patient can understand, correct any misconceptions and show strategies to critically assess digital health information. The patient will be asked to present their strategy to find updated reliable health information available on the Internet. The teach-back method aim to reveal topics where there is a need to further modify and/or repeat information to make it possible to understand for the patient.

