## **5.2 Randomization**

At baseline, patients will be randomized according to a randomization scheme (ratio 1:1 for intervention vs control generated by a Statistician at Akershus University Hospital) and administered by a co-worker at Akershus University Hospital who does not take part in the study. The PI, or any other member of the study group, plays no role in the randomization process and will not be given access to the randomization scheme during the recruitment period. There is no blinding procedure (open clinical trial).

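### The flowchart and the arm-specific text imply randomization before the website and video presentation that both arms share, so in this open trial its delivery can vary by arm

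*Protocol*

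**What the plan says.** Protocol section 4.1.2 makes the website presentation common to both arms: "All study participants will be presented to this source of health information at baseline and asked to study it closely". The synopsis names the element that is not common: "The teach-back method will be used in the intervention group only".

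On the order of steps, the flowchart in section 4.1.1 has a row for randomization and, directly beneath it, the row "Presentation of websites, including LNT information videos". Both are marked in the screening and baseline column. Section 4.1.2 says that the visits follow this flowchart. It opens the baseline visit with "At the baseline visit a semi-structured interview will be performed, followed by a presentation of the LNT website" and does not mention randomization there. It then turns to patients randomized to control and says that "the Investigator will present them with the information videos available at the LNT website". For patients randomized to the intervention, "the Investigator will take on a more active part and make a new appointment with the patient (a new study visit) within 7 days".

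Section 5.2 places randomization at baseline without naming the step within the visit. It has an independent co-worker administer the scheme, and it says of masking: "There is no blinding procedure (open clinical trial").

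**The concern.** The presentation is an active exposure. The videos cover how to judge digital health sources critically and where to find reliable ones, which is close to what eHEALS, the primary endpoint, is meant to measure. If the Investigator already knows the arm while presenting, a step that should be identical can become fuller or shorter by arm.

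The direction could go either way. No further contact is described for a control patient before the final visit, so the Investigator may do more at baseline. Equally, an Investigator who is about to book an intervention patient for teach-back may invest more in that patient from the start. A fuller presentation to controls would mask an effect of the intervention; a thinner one would mimic an effect. Section 5.3 compares change from baseline between arms with a t-test, and that analysis cannot separate such a difference from the effect of the intervention.

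**Working it through.** The main check is a reading of the text. The arithmetic at the end only gives a sense of scale.

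1. **Evidence for randomization first.** In the flowchart, the rows from screening through consent, interview, questionnaires, randomization, presentation and teach-back form a natural sequence, and section 4.1.2 ties the visits to that flowchart. The same section describes the presentation again as something done for patients already allocated to control.

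2. **Evidence that leaves the order open.** Both rows sit in one visit column and carry no times. The rows are not strictly chronological: the medical record assessment and the Charlson index, both marked at baseline, stand below the teach-back row, which falls within the next 7 days. The opening sentence of the baseline visit gives interview, then presentation, without placing randomization. Section 5.2 says only that it occurs at baseline.

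3. **Protection of the shared step.** Section 5.2 keeps the randomization scheme from the study group during recruitment. That prevents prediction of the next allocation. It does not keep an individual allocation from the Investigator once it has been assigned, and no other section does so until the presentation ends.

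4. **Need for this order.** Nothing requires it. Teach-back is a separate contact within 7 days, so the allocation is not needed to give the presentation.

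5. **Baseline scores.** The interview and all questionnaires are listed above randomization. If that order holds, baseline eHEALS is not affected.

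6. **Scale, on assumed shifts.** Section 5.1 uses N ≥ 8/f² + (m − 1) with f² = 0.05. With m = 1 this gives 8/0.05 = 160 completers, and 160 × 1.20 = 192 reproduces the stated sample size. At 1:1 allocation that is 160/2 = 80 completers per arm. In units of the SD of the change score, the standard error of the arm difference is √(2/80) = 0.158. Suppose the intervention has no effect, but uneven delivery shifts the difference by b SD. The chance of a significant result at a two-sided 5% level (the protocol does not state sidedness) is 1 − Φ(1.96 − b/0.158) + Φ(−1.96 − b/0.158):

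| Assumed shift b (SD) | Chance of a significant result |
|---|---|
| 0.05 | 6.2% |
| 0.10 | 9.7% |
| 0.20 | 24.4% |
| 0.30 | 47.5% |

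The values of b are assumptions. The protocol gives no basis for choosing among them.

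**The case against.** The strongest reply is that the order is inferred. A reader might say that the protocol states randomization comes first. It does not: the flowchart rows are untimed and partly out of sequence, and the opening text on the baseline visit is compatible with presentation first. This stands, and it is why the point is put as an implied order. It does not remove the need for a change, because even the lenient reading leaves the order open and the allocation unprotected.

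A reader might also infer that the comparison would be teach-back alone if only the order were right. The documents do not support that. Under section 4.1.2 the intervention arm also has an extra visit, a summary of take-home messages, a question session and an instruction before that visit: "The patient will be asked to seek information available at the LNT website and watch the information videos found at this website". Sections 2.3 and 4 describe the evaluated intervention as tailored information followed by teach-back. Those differences are intended and follow allocation by design; uneven delivery of the shared presentation is neither intended nor necessary.

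It can further be said that there is little room for uneven delivery, since the content is 20 pre-recorded videos and public websites. That limits the problem but does not close it: the live introduction, help with navigation, time spent and encouragement to study the site remain with the Investigator.

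Finally, much of the exposure is the patient's own viewing after the visit, when the arm is known under either order. This also stands, and it limits what the fix achieves.

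**Conclusion.** The point holds as an avoidable risk of performance bias in one shared component. The flowchart and the arm-specific wording imply randomization before the presentation, no section withholds the allocation until the presentation is over, and the trial is open. The protocol shows that delivery could differ by arm. It does not show that delivery did differ, or that all 192 presentations were affected.

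Size and direction cannot be estimated. A reader might want to express the possible bias as a share of the teach-back effect. That would be one assumption divided by another, because the protocol gives no SD for eHEALS and no expected effect on it, and section 5.1 itself says that its sample size does not rest on patient data. The table above shows only that a small assumed shift (0.05 SD) barely moves the error rate, while one of 0.20 SD or more would matter.

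I would class this as a cheap improvement: a specific, better order of steps at almost no cost.

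**What to change.** In sections 4.1.1, 4.1.2 and 5.2, set one order for the baseline visit:

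1. consent;
2. interview and questionnaires;
3. the website and video presentation, given in the same way to every patient;
4. randomization by the independent co-worker;
5. for intervention patients only, the teach-back appointment and the request to view the material before it.

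In the flowchart this means exchanging two adjacent rows. In section 4.1.2, describe the presentation once, before either arm is mentioned, so that it no longer reads as an act directed at controls. In section 5.2, state that the allocation is requested and disclosed only after the presentation has ended.

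The cost is small. The steps stay within the same visit and the person who administers randomization is already in place. A patient who leaves before the presentation ends would not be randomized, which narrows the randomized population slightly. The change protects the baseline presentation only. It does not equalise later self-directed viewing, which differs between the arms by design.

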#### **4.2 Storage of Study Documentation and Data Management**

The PI will arrange for the retention of the patient identification list. Patient files shall be kept for the maximum period of time permitted by Akershus University Hospital. The study documentation shall be retained and stored during the study and for five years after study closure in accordance with FOR 2009-30-10 §8. All information concerning the study will be stored in a safe place inaccessible to unauthorized personnel. Registration of patient data will be carried out in accordance with national personal data laws. Data will be coded and entered into a computer database according to operating procedure for data management provided by The Norwegian Research Council. The study will be conducted in accordance with the Declaration of Helsinki and are consistent with ICH/Good Clinical Practice and applicable regulatory requirements.

#### **4.3 Patient Withdrawal**

All study subjects have the right to withdraw from the trial at any time and this will in no way prejudice their future treatment, in accordance with the Declaration of Helsinki. We plan to follow the patients for the entire duration of the study. Unless patients who choose to withdraw from the study specifically requests not to be contacted, every effort will be made in order to follow-up and complete patient evaluation.

#### **4.4 Patient Confidentiality**

The Investigators will ensure that the patient's confidentiality is maintained throughout the study. The electronic CRF only identify patients by their randomization number. The PI will keep a separate log of patient codes and names. Akershus University Hospital provides a Study Monitor and any audits will be conducted with strict adherence to professional standards of confidentiality.

#### **4.5 Study Amendments**

Should it be necessary for the study protocol to be amended, the amendment will be notified to and sent for approval to local and national regulatory authorities (Personvern Akershus University Hospital and REK). The current Participant Information Form contains information about possible future amendments and need of a second consent before enrollment in future studies.

### **5 STATISTICAL CONSIDERATIONS**

#### **5.1 Determination of Sample Size**

There is no previous data from trials to base any power analysis on for this study, thus it is appropriate to base sample size calculation on Tabachnick and Fidells formula  $N \geq (8/f^2) + (m-1)$ , where  $f^2$  is set at 0.05, hence 160 patients need to complete the trial (23). With an expected drop-out rate of 20% the calculated sample size is 192. However, this estimate is solely based on mathematical principles and not patient observations. Thus, should concurrent studies performed on a related topic provide data on which we can base power analysis, we will ask REK for approval to adjust the sample size accordingly. In addition, we aim for inclusion of  $\geq 50$  patients with other native tongue than Norwegian, Swedish, Danish or English, as this is an important subgroup.

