## 3 STUDY POPULATION

### 3.1 Target Population, Number of Patients, Recruitment and Screening

The target population is patients with advanced kidney disease defined as CKD stage 4 or 5, including renal transplant recipients (defined as CKD5T), who receive health care at Akershus University Hospital. The sample size is set at n = 192, where we aim for inclusion of  $\geq 50$  patients with other native tongue than a Scandinavian language (Norwegian, Swedish or Danish) or English. Patients will be recruited from the Dialysis Unit, wards and outpatient clinic at the Department of Renal Medicine, Akershus University Hospital.

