## **5.3 Statistical Analysis**

All statistical tests will be performed using a 5% significance level unless otherwise stated. We will calculate delta values for efficacy variables (change from baseline to the final visit) for the intervention and control groups. The main statistical approach will be t-test for independent groups. For the composite end-point of positive SARS CoV2 test, hospitalization or death we will use odds ratio as the outcome measure.

Demographics and efficacy data will be summarized using means and standard deviations for normally distributed continuous variables, medians and interquartile range for non-normally distributed continuous variables and percentages for categorical variables.

Subgroup analysis will be performed according to (high vs low) educational level and modality of renal replacement therapy.

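### The drop-out allowance in Protocol section 5.1 is miscalculated: at 20% drop-out, 192 enrolled leave about 153 to 154 completers, not the required 160

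*Protocol*

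**What the plan says.** Protocol section 5.1 takes a textbook formula for the number of cases, N ≥ (8/f²) + (m − 1), with f² = 0.05, and concludes: "hence 160 patients need to complete the trial". The next sentence makes the allowance for losses: "With an expected drop-out rate of 20% the calculated sample size is 192". The figure is carried into the synopsis ("Sample Size: n = 192, where we aim for inclusion of" at least 50 patients with another native tongue) and into section 3.1 ("The sample size is set at n = 192").

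Section 5.1 also says that the estimate has no patient data behind it, and that approval to change the sample size will be sought if related studies supply data for a power analysis. Section 4.3 says that withdrawn patients will be followed up where they do not object to contact. No section gives a replacement rule, a second drop-out rate or another target for completers.

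**The concern.** A drop-out rate is ordinarily the share of enrolled patients who do not complete. To end with a given number of completers, that number is divided by one minus the rate. Multiplying by one plus the rate gives too few, and the gap widens as the rate rises. The figures in section 5.1 look like the second calculation.

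At stake is whether the planned enrolment delivers what the protocol says it needs. The main analysis in section 5.3 compares change from baseline to the final visit, and a patient without a final visit supplies no such value directly. Because the protocol has no power calculation, the step from 160 to 192 is a large part of the justification for n.

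**Working it through.** **Inputs**

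- f² = 0.05, completers required = 160, drop-out = 20%, planned enrolment = 192: Protocol section 5.1 (192 also in the synopsis and section 3.1).
- m, the number of predictors in the formula, is not stated.
- Allocation is 1:1 (section 5.2).

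**Step 1: reproduce the 160.** 8 / 0.05 + (m − 1) = 160 + (m − 1). The stated 160 follows with m = 1 (assumed); m = 2 would give 161. The check below takes the stated 160 as given.

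**Step 2: reproduce the 192.** 160 x (1 + 0.20) = 160 x 1.20 = 192. This matches exactly.

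**Step 3: the allowance that a 20% drop-out rate calls for.** 160 / (1 − 0.20) = 160 / 0.80 = 200, or 100 per arm. That is 200 − 192 = 8 more than planned.

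**Step 4: what 192 delivers.**

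| Quantity | Calculation | Result |
|---|---|---|
| Expected losses at 20% | 192 x 0.20 | 38.4 |
| Expected completers at 20% | 192 x 0.80 | 153.6 |
| Shortfall against 160 | 160 − 153.6 | 6.4 |
| Shortfall as a share of 160 | 6.4 / 160 | 4.0% |
| Losses that still leave 160 | 192 − 160 | 32 |
| The same as a drop-out rate | 32 / 192 | 16.7% |

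**Step 5: how likely 160 would be reached.** Assume that each patient independently has a 20% chance of dropping out. Completers then follow a Binomial(n, 0.80) distribution:

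- n = 192: P(at least 160) = 0.143, about 14%.
- n = 200: P(at least 160) = 0.542, about 54%.

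**Step 6: consequence for precision, as illustration only.** The protocol states neither power nor the sidedness of its 5% test. If f² = 0.05 is converted to a two-group standardised difference, d = 2 x √0.05 = 0.447, and a two-sided 5% t-test is assumed, power is about 80.3% with 80 per arm. It is about 78.5% with 77 and 76 per arm, and 78.7% with 77 and 77. The loss is under two percentage points.

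**The case against.** The best case on the other side concerns weight rather than arithmetic.

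- **The 160 is itself soft.** It comes from a rule of thumb with a chosen f², and the protocol says so. Under the same rule with m = 1, 153.6 completers correspond to f² = 8 / 153.6 = 0.052 instead of 0.050, a difference well within the arbitrariness of the input. No stated power is missed, because none is stated. This stands, and it limits the size of the problem. It does not make the step from 160 to 192 correct.
- **The sample size is open to revision.** That is true, but only if other studies supply data for a power analysis. It does not repair the drop-out allowance.
- **Some patients who withdraw may still be assessed.** Section 4.3 makes this possible, so 20% drop-out need not mean 20% missing outcomes. But section 5.1 counts patients who complete, and no number is attached to the recovery of withdrawn patients.
- **The 20% could be a margin on top of completers.** That reading yields 192 exactly, but the text calls it an expected drop-out rate and does not define it as a share of completers.

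It is also fair to say that the 14% sounds more alarming than an average shortfall of 6 to 7 patients, and that it depends on the independence assumption.

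**Conclusion.** The concern holds. The three figures in section 5.1 (160 completers, 20% drop-out, 192 enrolled) cannot all be right, and no other part of the protocol reconciles them. At its own drop-out rate the trial is expected to fall 4% short of its own completer requirement.

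This rests only on reading the drop-out rate as a share of those enrolled; it does not depend on m, on the binomial assumption or on the conversion to power. The error is certain and its effect modest. It does not compromise the trial, but the sentence that justifies the sample size should be corrected.

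**What to change.** Keep n = 192 and correct section 5.1 in one of two ways:

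- **Preferred:** replace the 20% with the rate that 192 supports, stating that 192 enrolled secures 160 completers provided drop-out is at most 16.7% (32 patients). This makes the three figures agree.
- **Alternative:** keep the 20% and state that it leaves about 153 completers. The neighbouring sentence that requires 160 to complete must then be reworded to match, or the contradiction remains.

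Either way the edit stays within section 5.1, needs no extra patients and leaves the synopsis and section 3.1 unchanged. The cost is a slightly less favourable stated margin for attrition. No power figure should be added.

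If the sponsor prefers to keep both 160 completers and 20% drop-out, n becomes 200. That costs 8 more patients and matching changes in the synopsis and section 3.1.
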